#### 7.6 Contraception

Patients with reproductive potential need to adhere to accepted and effective methods of birth control during treatment with immunotherapy and for at least 6 months after last administration. These include the oral contraceptive pill, hormonal injections or implants, an intrauterine device (IUD), bilateral tubal occlusion, vasectomy or sexual abstinence if this is your usual lifestyle choice. Male participants with WOCBP partners are required to use a condom.

#### 8 SAFETY AND PHARMACOVIGILANCE

#### 8.1 **Definitions**

#### 8.1.1 Adverse Events (AEs)

An adverse event is any untoward medical occurrence in a patient administered a drug; the event does not necessarily have a causal relationship with the treatment or usage.

The following should not be recorded as AEs if recorded as medical history/concomitant illness on the CRF at screening:

- Pre-planned procedure, unless the condition for which the procedure was planned has worsened from the first trial related activity after the subject has signed the informed consent.
- Pre-existing conditions found as a result of screening procedures unless the condition worsens from the first trial related activity after the subject has signed the informed consent.

Procedure for collecting Adverse Events

- For the purpose of this trial, any detrimental change in the patient's condition that
  occurs after the subject has started trial treatment, up to and including 95 days
  after last trial treatment should be considered an AE.
- All AEs regardless of their seriousness or relationship to the product should be recorded on the relevant Case Report Form (eCRF) from day 1 of treatment until 95 days after last treatment date. Investigator's assessment of the seriousness and causal relationship between the AE and the study medication should also be provided on the eCRF. AEs will continue to be followed until resolution or patient comes off trial.
- Whenever one or more signs and/or symptoms correspond to a disease or a welldefined syndrome only the main disease/syndrome should be reported. The severity of adverse events will be graded according to the NCI-CTC criteria (CTCAE v5.0).

#### 8.1.2 Serious Adverse Events (SAEs)

An SAE is any untoward medical occurrence or reaction that occurs after the commencement of treatment and within 95 days of the last administration of the trial regimen, that:

- · Results in death
- Is life threatening

Note: the term "life-threatening refers to an event/reaction in which the patient was at risk of death at the time of the event/reaction; it does not refer to an event/reaction which hypothetically might have caused death if it were more severe.

- Requires inpatient hospitalisation or prolongation of existing hospitalisation
- Is a congenital anomaly/birth defect; or
- Is a medically important event or reaction.

Note: Medical and scientific judgment should be exercised in deciding whether other situations should be considered serious, such as important medical events that might not be immediately life-threatening or result in death or hospitalisation, but might jeopardise the patient or might require intervention to prevent one of the other outcomes listed in the definition above.

The following list of medically important events is intended to serve as a guideline for determining which conditions should be considered as a medically important event. The list is not intended to be exhaustive:

- Intensive treatment in an emergency room or at home for:
- Allergic bronchospasm
- Blood dyscrasias (i.e., agranulocytosis, aplastic anaemia, bone marrow aplasia, myelodysplasia, pancytopenia, etc.),
- Convulsions (seizures, epilepsy, epileptic fit, absence, etc.).
- Development of drug dependence or drug abuse
- Alanine aminotransferase (ALT) >3 x ULN + total bilirubin >2 x ULN or asymptomatic ALT increase >10 x ULN
- Suicide attempt or any event suggestive of suicide
- Syncope, loss of consciousness (except if documented as a consequence of blood sampling)
- Bullous cutaneous eruptions
- Cancers diagnosed during the study or aggravated during the study (only if judged unusual/significant by the Investigators in oncology studies)
- Chronic neurodegenerative diseases (newly diagnosed) or aggravated during the study (only if judged unusual/significant by the Investigators in studies assessing specifically the effect of a study drug on these diseases).
- Suspected transmission of an infectious agent: if any suspected transmission of an infectious agent via a medicinal product (e.g., product contamination)
- Required intervention to prevent permanent impairment or damage related to device use.

The following events should be immediately reported to the Marketing Authorisation holder by the chief investigator.

- Pregnancy
- Overdose both serious and non-serious with the IMP

In this patient population disease progression itself is not considered to be an AE, unless the investigator believes the progression is atypical or possibly related to the IMP. However, if progression is accompanied by an untoward medical occurrence that is experienced within 95 days of the last treatment dose this should be recorded as an AE as specified in section 8.1.1 or as an SAE if it meets the criteria as per section 8.1.2.

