#### Outcome Categories and Definitions for SAEs:

- Resolved: Fully recovered or by medical or surgical treatment the condition has returned to the level observed at the first trial related activity after the subject signed the informed consent
- Resolved with sequelae: As a result of the AE, the subject suffered persistent and significant disability/incapacity (e.g. became blind, deaf, paralysed). Any AE recovered with sequelae should be rated as an SAE
- Ongoing
- Died
- Unknown

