# 8.4 Reporting of Serious Adverse Events/Reactions to the Sponsor

These will be recorded and reported in accordance with the sponsor's Safety Reporting SOP.

Serious adverse events should be reported using the initial SAE form. They require immediate reporting by email to the sponsor within 24 hours of a member of the research team becoming aware of the event. Additionally any SAE which the

investigator considers related to the IMP i.e. a SAR must be reported as above even if more than 95 days have elapsed from the date of last treatment.

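### The SAE definition in 8.1.2 leaves out disability, which the outcome categories under 8.3 treat as serious, so 24-hour reporting of an ongoing disabling event can rest on discretion

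*Protocol*

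**What the plan says.** Protocol 8.1.2 defines an SAE by five criteria, applied from the start of treatment to 95 days after the last administration:

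- "Results in death"
- "Is life threatening"
- "Requires inpatient hospitalisation or prolongation of existing hospitalisation"
- "Is a congenital anomaly/birth defect; or"
- "Is a medically important event or reaction"

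A note to the last criterion asks for medical and scientific judgment. It covers events that may put the patient in jeopardy, or that "might require intervention to prevent one of the other outcomes listed in the definition above". A list of examples follows and is expressly not exhaustive.

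The outcome categories that follow the causality table in 8.3 define resolution with sequelae by persistent and significant disability or incapacity, with blindness, deafness and paralysis as examples. They add: "Any AE recovered with sequelae should be rated as an SAE". A separate category for ongoing events carries no such rule.

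Section 8.4 requires SAEs to reach the sponsor "within 24 hours of a member of the research team becoming aware of the event".

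**The concern.** The protocol takes the position that lasting disability makes an event serious, but leaves it out of the section that decides seriousness. Where it does appear, it depends on the final outcome, whereas expedited reporting has to start when the harm is recognised.

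Seriousness opens each later step in the safety chain:

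- the 24-hour report (8.4);
- the Chief Investigator's review of causality and expectedness (8.5);
- SAR and SUSAR status (8.1.5, 8.1.6) and the 7-day or 15-day report to the MHRA (8.6);
- the annual safety report, which includes all SARs and SUSARs (8.8);
- the number of SAEs, one of only two safety statistics named in 11.4.

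An event not classed as serious at the first step misses all of them. Safety and tolerability is a secondary endpoint (2.3). The protocol also foresees events of this kind: 7.5.4 names neurological toxicity and 7.5.3 names paralysis among infusion symptoms.

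**Working it through.** No figure in the plan bears on this point and no arithmetic applies. The check sets the sections side by side and follows one event through them.

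| Place | Does disability make the event serious? | When? |
|---|---|---|
| 8.1.2, five criteria | Not named | – |
| 8.1.2, examples of medically important events | Not named; the nearest item concerns intervention to prevent impairment related to device use | – |
| 8.3, outcome resolved with sequelae | Yes | Once the event has that outcome |
| 8.3, outcome ongoing | No rule | – |

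**The list.** Of the five criteria, none names disability or incapacity. The fourth ends with the conjunction that introduces the last item, so the list reads as complete. There is no gap or redaction mark where a criterion could have been lost.

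**The test event.** Take a disabling event that is ongoing, does not threaten life and does not lead to admission.

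1. Death, threat to life, admission and birth defect are not met.
2. Medical importance has two limbs. The second refers to preventing the outcomes listed in the definition; disability is not one of them, so this limb gives no route by way of disability. The first limb, jeopardy to the patient, remains and is a matter of judgment. The device example does not help, because the trial tests a drug.
3. The rule under 8.3 does not apply, because the event has not recovered with sequelae. Under 8.1.1, AEs are followed until resolution or until the patient comes off trial, so an event can stay in the ongoing category throughout.

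The event is therefore an SAE only if the investigator chooses to call it medically important.

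**Does 8.3 repair the gap?** Its outcome categories are headed as applying to SAEs, that is, to events already classed as serious. A site that has screened an event out under 8.1.2 has little reason to consult them. For events that accompany progression, the end of 8.1.2 points back to its own criteria and not to 8.3.

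**Timing when 8.3 does apply.** If the event is first rated serious at its recorded outcome, the protocol does not say whether the 24 hours in 8.4 run from awareness of the event or from the re-rating. Section 8.7 expects the first follow-up report 10 days from onset. An event re-rated more than 10 days after onset would have its follow-up report fall due before its initial report existed.

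**The case against.** The strongest reply is that the medical-importance criterion already covers such events. It is a listed criterion, its note tells investigators to use judgment, its jeopardy limb is not tied to the listed outcomes, and its examples are not exhaustive. Few investigators would regard new blindness or paralysis as not serious. This stands to the extent that reporting is possible and in a clear case likely. It does not make reporting required, and the protocol should not leave to discretion what it states as a rule under 8.3.

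Second, such an event would not vanish. Section 8.1.1 requires every AE on the eCRF, with the investigator's view of seriousness and causality, up to 95 days after last treatment. If it is grade 3 or 4 while on treatment, it enters the other safety statistic in 11.4. This stands, and it limits the harm to expedited reporting, the steps that follow from it and the SAE count. An eCRF entry triggers none of these.

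Third, the sponsor's Safety Reporting SOP and the SAE form, both named in 8.4, are not shown and may list disability. If so, the practical gap is smaller, but the protocol would still disagree with itself and with those documents.

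**Conclusion.** The concern holds. Sections 8.1.2 and 8.3 treat disability differently, and a disabling event that is ongoing, not life-threatening and not admitted falls between them unless it is judged medically important.

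The size cannot be derived, because the protocol gives no expected rate for such events. A percentage per patient would not help either, since 11.4 reports SAEs as a number. The group is narrow, and the primary endpoint and the interim rule are unaffected. The conclusion rests on the protocol text alone and assumes nothing about the SOP or the SAE form. The correction should be made because lasting harm is at stake and the change is small.

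**What to change.** Add to the list in 8.1.2 a criterion that the event results in persistent or significant disability or incapacity. Use the same wording under 8.3, where the two adjectives are now joined by 'and', so that both places set the same threshold. State that the 24 hours in 8.4 run from recognition of the disability, whatever outcome is later recorded. The sentence under 8.3 on sequelae can then stay as a cross-check.

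Check that the SAE form and the Safety Reporting SOP carry the same criterion, and amend them if they do not.

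The cost is one bullet, a matching edit under 8.3, a clarifying sentence in 8.4, possibly one box on the form, and perhaps a few more SAE reports. Treatment and patient management do not change.

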#### 8.1.3 Adverse Reaction (AR)

There is a reasonable possibility according to the investigator and/or the sponsor that the Product may have caused the adverse event.

#### 8.1.4 Unexpected AR

An adverse reaction (AR) is considered unexpected if the nature, severity, specificity, or outcome is not consistent with the term or description used in the reference safety information (RSI). This can be found in the cemiplimab investigator brochure edition 09 (21/04/2022) (section 6.4). An expected AR with a fatal outcome should be considered unexpected.

# 8.1.5 Serious Adverse Reactions (SAR)

A serious related adverse event i.e. adverse reaction (SAR) is an SAE that has a definite, probable or possible causal relationship to the trial drug.

#### 8.1.6 Suspected Unexpected Serious Adverse Reactions (SUSARs)

Any adverse reactions that have a suspected relationship to the trial drug that are both serious and unexpected, as judged by the Investigator.

An unexpected serious adverse reaction is one that is not listed as a known toxicity of the investigational drug in the RSI.

# 8.2 **Pregnancy**

Pregnancy occurring in a female patient or female partner of a male patient during the study or within 180 days of the last dose of study drug must be reported to the ILS team within 1 working day of identification using the pregnancy eCRF. Pregnancy per se is not considered as an AE however any complication of pregnancy affecting a female study patient or female partner of a male study patient, and/or fetus and/or newborn must be reported as an SAE. Outcomes for all pregnancies should be reported to the sponsor.

#### 8.3 Causality (relatedness)

Investigators must assess whether there is a reasonable causal relationship with the IMP administered, or with the study procedure(s), for each reported AE. "Reasonable causal relationship" means that there are facts/evidences or arguments to suggest a causal relationship [based on ICH E2A Guideline].

- Associated to investigational product
- Not associated to investigational product

The assignment of causality for serious adverse events should be made by the investigator responsible for the care of the patient and delegated by the PI the task of undertaking causality assessment, using the definitions in Table 2 (below). If there is any doubt about the causality the investigator should assume that it is related until further information becomes available.

Table 2 Definitions for causality

Relationship	Description
Unrelated	There is no evidence of any causal relationship with the trial drug
Unlikely	There is little evidence to suggest there is a causal relationship (e.g. the event did not occur within a reasonable time after administration of the trial medication). There is another reasonable explanation for the event (e.g. the patient's clinical condition, other concomitant treatment)
Possible	There is some evidence to suggest a causal relationship (e.g. because the event occurs within a reasonable time after administration of the trial medication). However, the influence of other factors may have contributed to the event (e.g. the patient's clinical condition, other concomitant treatments)
Probable	There is evidence to suggest a causal relationship, and the influence of other factors is unlikely
Definitely	There is clear evidence to suggest a causal relationship, and other possible contributing factors can be ruled out
Not assessable	There is insufficient or incomplete evidence to make a clinical judgement of the causal relationship

#### Outcome Categories and Definitions for SAEs:

- Resolved: Fully recovered or by medical or surgical treatment the condition has returned to the level observed at the first trial related activity after the subject signed the informed consent
- Resolved with sequelae: As a result of the AE, the subject suffered persistent and significant disability/incapacity (e.g. became blind, deaf, paralysed). Any AE recovered with sequelae should be rated as an SAE
- Ongoing
- Died
- Unknown

# 8.4 Reporting of Serious Adverse Events/Reactions to the Sponsor

These will be recorded and reported in accordance with the sponsor's Safety Reporting SOP.

Serious adverse events should be reported using the initial SAE form. They require immediate reporting by email to the sponsor within 24 hours of a member of the research team becoming aware of the event. Additionally any SAE which the

investigator considers related to the IMP i.e. a SAR must be reported as above even if more than 95 days have elapsed from the date of last treatment.

**AND** 

The ILS team [contact]

Forms must be completed, signed and dated by the site Principal Investigator or delegated clinician. Any missing information from the initial SAE form must be provided within 72 hours of the first report.

#### 8.5 Review of Serious Adverse Events/Reactions

Events reported using the SAE form will be forwarded to the Chief Investigator (CI) immediately (or designated representative) for assessment of causality and expectedness. The CI can upgrade an investigator assessment of expectedness from unrelated to related for purposes of regulatory reporting but can never downgrade the expectedness from related to unrelated.

Centres should respond as soon as possible to requests from the CI or designated representative (via the sponsor) for further information that may be required for final assessment.

#### 8.6 Expedited Reporting of SUSARs

If an SAE/SAR is defined as a SUSAR (both related and unexpected and is fatal or life threatening, the sponsor will report this to the MHRA within 7 days from the date of being notified of the event.

If an SAE/SAR is defined as a SUSAR and is not fatal or life threatening, the sponsor will report this to the MHRA within 15 days.

The main REC must be informed of all SUSARs within the same timeframes detailed above and this responsibility is delegated by the sponsor to the BHOC-CTU ILS team.

The Principal Investigator at all actively recruiting centres will be informed by the ILS team of any SUSARs occurring within the trial.

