#### Treatment

Up to 34 cycles of treatment with cemiplimab alone (maximum of 24 months of treatment)

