#### 3 TRIAL DESIGN

This is a non-randomised, open, single arm, two-stage, multi-centre phase II trial evaluating efficacy of cemiplimab (continue until progression) in patients with IaBCC.

The trial aims to recruit 41 patients with laBCC, who will receive the following regimen:

cemiplimab 350mg on day 1 only of each 21 day cycle, over a maximum period of 2 years.

Assessment of response will be done after cycle 4 and then every 12 weeks whilst on trial and progression free.

The planned recruitment duration for this study is 2 years. Patients will have up to 24 months of treatment and will be followed for a further 24 months after treatment ends at 3, 6, 9, 12, 18 and 24 months.

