# 10 END OF STUDY (EOS)

Recruitment is planned for 24 months. Patients will be treated for up to 24 months and then followed up every 3 months for a further 12 months. Survival follow up will then be conducted at 18 and 24 months post end of treatment. The end of study is defined as last patient last visit (LPLV) which will be the last survival follow up visit (at 24 months after end of treatment) completed by a patient on the trial.

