#### 12.1.1 Responsibilities

The study will be performed subject to favourable opinion/ authorisation/permission or equivalent from all necessary regulatory and other bodies. This includes but is not limited to REC, MHRA, HRA, NHS trusts.

UHBW has sponsorship responsibility for obtaining authorisation and appropriate research ethics committee (REC) opinion (Part 3 of the Regulations) and for pharmacovigilance (Part 5 of the Regulations).

The sponsor warrants that the Study will be performed in compliance with all applicable local and international laws and regulations, including without limitation ICH E6 guidelines for Good Clinical Practices.

The sponsor shall be responsible for the respect of all obligations required by applicable local and international laws and regulations.

The sponsor shall be responsible for all required periodic updates to the health authorities and expedited reporting of all Serious Adverse Events occurring during the performance of the study, in accordance with local and regional regulations.

The sponsor shall also be responsible to provide to the investigators and the Ethics Committee all relevant study related information (including information submitted to the Health Authorities and any "Dear Investigator Letter" received from Sanofi.

The sponsor must report the following information in English to the Sanofi Pharmacovigilance contact:

- Copy of all individual Suspected (drug related) and Unexpected Serious Adverse
   Reactions (SUSARs) at time of submission to MHRA and REC (format sent to
   MHRA and REC) or, if submission of SUSAR is not required in the participating
   country, such individual reports shall be sent to Sanofi on an ongoing basis.
- In addition to SUSARs, any other events that have been submitted to the MHRA and REC according to local regulatory requirements in the participating country shall be sent to Sanofi at time of submission to these bodies.
- Any significant safety issues, events or results, e.g., Data Safety Monitoring Board recommendations, occurring or found during the course of the Study which might affect performance thereof shall be sent to Sanofi on an ongoing basis.

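### Section 8.6 ties SUSAR notices to recruitment status, so its recipient list leaves out centres that have stopped recruiting but still have patients on cemiplimab, and it is narrower than the duty in section 12.1.1

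*Protocol*

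**What the plan says.** Section 8.6 of the protocol gives the reporting times to the regulator and the ethics committee (7 days for a fatal or life-threatening SUSAR, 15 days otherwise) and then turns to the sites: "The Principal Investigator at all actively recruiting centres will be informed by the ILS team of any SUSARs occurring within the trial". It names a sender, the ILS team, and a recipient group defined by recruitment status. It sets no deadline for this notice.

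Section 12.1.1 states a broader obligation: "The sponsor shall also be responsible to provide to the investigators and the Ethics Committee all relevant study related information". The same sentence makes clear that this takes in material sent to the health authorities. It refers to the investigators without regard to recruitment status. It names the sponsor as responsible, but gives no route and no deadline.

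The trial calendar is in section 10: "Recruitment is planned for 24 months. Patients will be treated for up to 24 months and then followed up every 3 months". The treatment limit is in the trial summary, "Up to 34 cycles of treatment with cemiplimab alone (maximum of 24 months of treatment", and again in section 3, "cemiplimab 350mg on day 1 only of each 21 day cycle, over a maximum period of 2 years". Section 5 asks for treatment to start within 3 weeks of registration. Sections 7.5 and 8.1.1 collect adverse events until 95 days after the last treatment.

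**The concern.** Recruitment status is the wrong test for a safety notice. The investigators who most need to know of a new unexpected serious reaction are those with patients on the drug or recently off it. While a centre is recruiting, the two groups largely coincide. They separate when a centre stops recruiting early and, for the whole trial, once recruitment closes. Read by itself, the 8.6 list shrinks as centres close and is then empty, although treatment goes on.

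Site investigators keep working through that period. They assess toxicity before each cycle (section 6.2), judge causality (section 8.3), decide on delay or discontinuation (sections 7.5.2 and 7.5.4) and seek continued consent at each visit (section 16). All of this is better done with prompt knowledge of SUSARs elsewhere in the trial. Section 8.6 is the only place in the protocol that says who sends the notice and to whom, so its wording matters in practice.

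**Working it through.** **1. Is the treatment limit consistent with itself?** Trial summary: 34 cycles. Section 3: 21 days per cycle. 34 × 21 = 714 days. At 365.25/12 = 30.44 days per month this is 23.5 months, which agrees with the stated maximum of 24 months.

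**2. How long can treatment run after recruitment closes?** Take a patient registered on the last recruitment day who starts 3 weeks (21 days) later.
- No delays: first to last dose is 33 × 21 = 693 days, so the 34th dose falls 21 + 693 = 714 days, or 23.5 months, after closure.
- Using the 24-month cap instead: 24 + 21/30.44 = 24.7 months after closure.

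**3. When does adverse event collection end?** Add 95 days.
- No delays: (714 + 95)/30.44 = 26.6 months after closure.
- With the cap: 24 + (21 + 95)/30.44 = 27.8 months after closure.

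**4. How much drug exposure falls after closure?** The protocol gives neither an accrual pattern nor an expected time on treatment, so both are assumed here: uniform entry over T = 24 months, treatment capped at T, constant discontinuation hazard k, and the start lag ignored.
- Mean exposure per patient: (1 − e^(−kT))/k.
- Mean exposure after closure: [(1 − e^(−kT))/(kT) − e^(−kT)]/k.
- Share after closure: [(1 − e^(−kT))/(kT) − e^(−kT)] / (1 − e^(−kT)).

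| Assumed time on treatment | kT | e^(−kT) | Share after closure |
|---|---|---|---|
| All complete 24 months | → 0 | → 1 | 12/24 = 50% |
| Median 12 months | 1.386 | 0.25 | (0.541 − 0.25)/0.75 = 39% |
| Median 6 months | 2.773 | 0.0625 | (0.338 − 0.0625)/0.9375 = 29% |

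**5. The two sections side by side.**

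| | Section 8.6 | Section 12.1.1 |
|---|---|---|
| Content | SUSARs in this trial | Relevant study information, including what goes to the health authorities |
| Recipients | Principal Investigators at recruiting centres | The investigators, without restriction |
| Who acts | ILS team | Sponsor |
| Route and deadline to sites | None stated | None stated |

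Under 8.6 every SUSAR is sent to the MHRA, so SUSARs come within 12.1.1. The recipients in 8.6 are therefore a subset of those owed the information under 12.1.1.

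**6. Does another section close the gap?** The annual safety report goes to the MHRA and the main ethics committee (8.8). The IDMC reports to the TSC and TMG (13.3), and Principal Investigators join the TMG as appropriate (13.1). None of these is a SUSAR notice to every treating centre.

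**The case against.** The strongest reply is that section 12.1.1 already covers the case. Its duty is owed to all investigators, expressly includes material sent to the health authorities, and does not lapse when recruitment ends. Section 8.6 states a duty towards one group and does not say that others are excluded. Both duties can be met at once, so they differ in breadth without contradicting each other. Section 8.4 also refers to a sponsor Safety Reporting SOP that is not available here and may set out a fuller circulation.

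Most of this stands, and it rules out several stronger readings. A reader might infer that SUSARs go solely to recruiting centres, or that no investigator would be told once recruitment closes. The protocol as a whole does not support either. A reader might also infer that safety ascertainment would differ before and after closure. It would not follow: adverse events are collected under one rule for every patient, from day 1 to 95 days after the last treatment, whatever the centre's recruitment status.

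The reply does not rescue the wording of 8.6. The sentence that assigns the task and defines the mailing list still uses the wrong criterion, and the general duty supplies no procedure of its own.

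**Conclusion.** The recipient definition in 8.6 is too narrow for the protocol's own calendar and does not match 12.1.1. It leaves out centres that may have patients on cemiplimab for about 24 months after recruitment closes (23.5 to 24.7 months, given a 3-week start lag) and under adverse event collection until about 26.6 to 27.8 months. The same gap applies earlier to any centre that stops recruiting while its patients are still on treatment.

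The 29% to 50% range rests on the assumed uniform accrual and treatment durations. It might be read as the proportion of SUSARs that would go unreported to sites. It is not: it describes only how much time on drug falls after closure, and under 12.1.1 no SUSAR should be withheld from investigators.

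This is a low-severity correction to safety-reporting wording. It has no effect on the endpoint, sample size, error rates or analysis.

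**What to change.** In section 8.6, replace the phrase limiting the notice to recruiting centres with: *all centres open to recruitment or with any patient on treatment or in trial follow-up*. A cross-reference to section 12.1.1 would make clear that 8.6 is how the sponsor's general duty is carried out for SUSARs. If the Safety Reporting SOP repeats the narrower list, align it as well.

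The cost is one sentence in the next amendment and a slightly longer distribution list. No dose, treatment rule, data collection or analysis changes.
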